8.3.6 Progression-Free Survival

Progression-free survival (PFS) is defined as the duration of time from start of treatment to time of progression per RECIST1.1 or death whichever comes first. PFS for patients who are not progressed at the time of data analysis will be censored on the date of the latest tumor assessment. Patients who go off treatment and begin alternate therapy, prior to progressing on this protocol will be censored at the time on the date of the latest tumor assessment before starting the alternate therapy. We assume that all patients have radiographic scans during screening period and before starting treatment. The following table describes how PFS event is defined and PFS time is calculated. Only radiographic scans used to tumor assessment per RECIST 1.1 before starting the alternate therapy will be counted if patients go off treatment and begin alternate therapy. The following table shows how PFS is defined in various scenarios (*Table 8.3.2*).

Scenario	PFS event (1) or censor (0)	PFS time
At least one post treatment scan is available and tumor response is evaluated according to RECIST 1.1 and all scans are completed on the schedule or off the schedule within a month and patient is alive at the latest follow-up.	1 if PD 0 if no PD	The date of the latest tumor assessment – the date of starting treatment

Table 8.3.2 Definition of PFS

At least one post treatment scan is available and tumor response is evaluated according to RECIST 1.1, but the gap between radiographic scans is greater than 3 months. No PD is observed on the latest scan before the gap occurs.	0	The date of the latest tumor assessment before the gap– the date of starting treatment
No disease progression per RECIST 1.1 is observed on the post-treatment scans and patient dies before the next scheduled scan + 1 month.	1	The date of death – the date of starting treatment
No disease progression per RECIST 1.1 is observed on the post-treatment scans and patient dies. The period from the latest scan to death is greater than 3 months.	0	The date of the latest tumor assessment – the date of starting treatment
No post-treatment scan is available and patient dies before the first scheduled scan + 1 month.	1	The date of death – the date of starting treatment
No post-treatment scan is available and patient is lost follow up or patient dies >3 months later after starting treatment.	0	0

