4.9 Treatment Beyond Progression

A minority of subjects treated with immunotherapy may derive clinical benefit either delayed responses, stable disease, or increased overall survival despite initial evidence of progressive disease (PD) with nivolumab or combination treatment.

Subjects may be permitted to continue treatment beyond initial RECIST 1.1-defined PD as long as the following criteria are met:

• Patients must be clinically stable with no change in performance status due to disease progression.

- No indication for immediate alternative treatment
- Patient [assessed by the investigator] is showing clinical benefit and tolerates study drug. The assessment of clinical benefit should take into account whether the subject is clinically stable or deteriorating and likely or unlikely to receive further benefit from continued treatment
- The time of progression is noted from the first assessment that exceeds standard criteria All decisions to continue treatment beyond initial progression must be discussed with the PI in advance, including if for any exception to the criteria noted above.

New lesions are considered measurable at the time of initial progression if the longest diameter is at least 10 mm (except for pathological lymph nodes, which must have a short axis of at least 15 mm). Any new lesion considered non-measurable at the time of initial progression may become measurable and therefore included in the tumor burden measurement if the longest diameter increases to at least 10 mm (except for pathological lymph nodes, which must have an increase in short axis to at least 15 mm).

For statistical analyses that include the investigator-assessed progression date, subjects who continue treatment beyond initial investigator-assessed, RECIST 1.1-defined progression will be considered to have investigator-assessed progressive disease at the time of the initial progression event. Subjects who have tumor shrinkage following RECIST-defined progression (e.g., irRC) will be also summarized separately.

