8.3.3 Evaluation of Best Overall Response

The best overall response is the best response recorded from the start of the treatment until disease progression/recurrence (taking as reference for progressive disease the smallest measurements recorded since the treatment started).

The subject's best response assignment will depend on the achievement of both measurement and confirmation criteria (*Table 8.3.1*).

Target	Non-Target	New	Overall	Best Overall Response when
Lesions	Lesions	Lesions	Response	Confirmation is Required ¹
CR	CR	No	CR	

Table 8.3.1 For Subjects with Measurable Disease (e.g., Target Disease)

CR	Non-CR/Non-PD	No	PR	
CR	Not evaluated	No	PR	>4 wks confirmation
PR	Non-CR/Non- PD/not evaluated	No	PR	
SD	Non-CR/Non- PD/not evaluated	No	SD	Documented at least once >4 wks. from baseline
PD	Any	Yes or No	PD*	
Any	PD**	Yes or No	PD*	no prior SD, PR or CR
Any	Any	Yes	PD	

*A minority of subjects treated with immunotherapy may derive clinical benefit either delayed responses, stable disease, or increased overall survival despite initial evidence PD with nivolumab or combination treatment.

Subjects may be permitted to continue treatment beyond initial RECIST 1.1-defined PD (see **Section 4.9**). In these cases, a radiological assessment will be repeated 4 weeks later to confirm or not the progression disease, as defined by RECIST criteria.

** In exceptional circumstances, unequivocal progression in non-target lesions may be accepted as disease progression.

NOTE: Subjects with a global deterioration of health status requiring discontinuation of treatment without objective evidence of disease progression at that time should be reported as "symptomatic deterioration;" (e.g., weight loss >10% of baseline body weight; worsening of tumor-related symptoms, decline in performance status >1 left on ECOG scale) after discussion with IND Sponsor. Every effort should be made to document the objective progression even after discontinuation of Treatment.

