NOTE: If applicable, the daily dose of entinostat may occur prior to hematology/chemistry tests and these laboratory tests may be drawn at the same time as the correlative blood samples.

- ^{19.} A third mandatory biopsy will be performed at week 6 from Cycle 1, Day1. A window of +14 days applies to this time point
- ^{20.} An optional biopsy will be performed at the time of disease progression.
- ^{21.} Archival tumor specimens from previously collected samples will be obtained for correlative analysis, if available.
- ^{22.} Weekly assessments for toxicity/adverse events may occur by phone on days when entinostat alone is administered. Additionally, assessments are to continue for 30 days after the last dose of nivolumab (at intervals <21 days) or to resolution of drug-related AEs to \leq Grade 1, whichever occurs later. SAEs that occur within 100 days of the last treatment or before initiation of a new antineoplastic treatment should also be followed and recorded. These may occur by phone for subjects no longer being seen at the institution; however, an in-person clinic visit may be needed to confirm event resolution and/or to effectively evaluate possible immune-related events. Subjects must be told of follow-up requirements at study entry.
- ^{23.} Subjects who complete or discontinue from treatment because of progression disease will be followed (by phone or email) every three months (+/- 2 weeks) after completion of the EOT visit for up to 2 years or study closure to monitor overall survival. Information of other cancer therapies after discontinuation from the study treatment will also be collected.

For subjects who discontinue treatment for reasons other than tumor progression, will be contacted (by phone or email) every three months (+/- 2 weeks) after completion of the EOT for up to 2 years or study closure to monitor overall survival, and information

93

about disease status will be also collected if possible (i.e. radiological imaging and/or tumor markers) until documented tumor progression.

NOTE: For evaluation of PFS, all subjects who discontinue study drug administration prior to 6 months must have restaging scans/imaging within a 7 day window of the 6 month time point from the date of initiation of combination treatment

J1798/Version 5.0/May 21, 2020

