12.3.2 Analysis of Secondary Endpoints

- OS is defined as the duration of time from start of study treatment to time of death. For subjects lost to follow-up or whose vital status is unknown, every effort will be made to determine the date such subjects were last known to be alive. Such efforts may include phone calls, certified mail, and the checking of public records. Subjects who are alive or lost to follow-up as of the data analysis cutoff date will be right-censored. The censoring date will be determined from the date the subject was last known to be alive.
- PFS is defined as the time from cycle 1, day 1 of immunotherapy until first documented local progression or death due to any cause. Disease progression will be assessed using RECIST (version 1.1). Due to the expectation that some patients may experience delayed clinical responses to therapy, patients with disease progression by radiographic imaging or laboratory parameters during a 12-week evaluation period but without rapid clinical deterioration or significant change in performance status that requires additional immediate therapy may continue to receive treatment on study.

Subjects that meet the above criteria and continue on study therapy must discontinue treatment upon documentation of disease progression on the second scan. The date of progression will be backdated to the time of first RECIST criteria progression. Tumor assessments will be made using RECIST 1.1 and immune-related response criteria (irRC). Individuals will be censored at the date of the last scan for PFS if no event occurs.

Median time to event will be calculated and reported with confidence intervals.

Analysis of PFS will be restricted to evaluable individuals who complete at least one dose of entinostat, while the analysis of OS will be performed on all evaluable patients.

OS curves, OS medians with 95% CIs, and OS rates at 6, 12, 24 and 36 months with 95% CIs will be estimated using Kaplan-Meier methodology

PFS curves, PFS medians with 95% CIs, and PFS rates at 6, 12 and 24 months with 95% CIs will be estimated using Kaplan-Meier methodology.

• Duration of response (DOR) will be calculated for subjects who achieve a best overall response of CR or PR with entinostat in combination with nivolumab. For such subjects,

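### Table 8.3.2 dates a RECIST progression at the latest scan and has no row for progression followed by death, contradicting the protocol's own first-progression rule for PFS

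*Combined protocol and SAP*

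**What the plan says.** Section 8.3.6 defines PFS as the "duration of time from start of treatment to time of progression per RECIST1.1 or death whichever comes first". It then hands the operational detail to Table 8.3.2: "The following table describes how PFS event is defined and PFS time is calculated".

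Row 1 of that table applies when at least one post-treatment scan has been evaluated, "all scans are completed on the schedule or off the schedule within a month and patient is alive at the latest follow-up". It codes an event for PD and a censored observation for no PD, and gives both the same time: "The date of the latest tumor assessment – the date of starting treatment". The text above the table counts only scans made before any alternate therapy.

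Other sections fix the progression date differently:

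- Section 4.9: patients treated past progression "will be considered to have investigator-assessed progressive disease at the time of the initial progression event".
- Section 6.2.1: the date entered on the end-of-treatment form is the one on which PD was first documented.
- Section 12.3.2: PFS runs to the first documented progression or death, and for patients kept on therapy, "The date of progression will be backdated to the time of first RECIST criteria progression".

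The protocol also plans imaging that can follow progression. Under section 8.3.3, when treatment continues past PD, a "radiological assessment will be repeated 4 weeks later to confirm or" refute it. The note to footnote 23 of the Study Calendar says that, for PFS, "all subjects who discontinue study drug administration prior to 6 months must have restaging scans/imaging within a 7 day window" of the 6-month point of combination treatment.

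**The concern.** For a censored patient the latest assessment is the right date. For a patient with PD it is right only if no countable scan follows the first one showing PD. Because the protocol plans such scans, row 1 can date the event later than sections 4.9, 6.2.1 and 12.3.2 do.

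The second gap is the requirement that the patient be alive. A patient with PD on a timely scan who later dies meets the text definition of an event but has no row in the table.

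At stake are the PFS curves, the median, and the rates at 6, 12 and 24 months, all planned secondary results. Two analysts, one following the table and one the text, could report different values from the same data.

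**Working it through.** **1. The six rows against the course PD on a scan, then death**

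| Row | Condition that matters | Covers it? |
|---|---|---|
| 1 | PD or no PD, patient alive | No |
| 2 | Gap over 3 months, no PD before it | No |
| 3 | No PD, death before next scheduled scan + 1 month | No |
| 4 | No PD, death over 3 months after last scan | No |
| 5 | No post-treatment scan, early death | No |
| 6 | No post-treatment scan, lost or later death | No |

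**2. Dates for one patient**

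Inputs: 2-week entinostat lead-in (4.1); scans every 8 weeks from cycle 1 day 1 (Study Calendar, footnote 2); repeat scan 4 weeks after PD (8.3.3); 6-month scan at about combination week 26 (footnote 23). Row 1 counts from the start of treatment, taken here as the first entinostat dose, so weeks = combination week + 2.

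| First PD, combination week | First-PD date | Row 1, 4-week repeat scan is latest | Row 1, 6-month scan is latest |
|---|---|---|---|
| 8 | 10 | 14 | about 28 |
| 16 | 18 | 22 | about 28 |
| 24 | 26 | 30 | not applicable (repeat scan is later) |

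For PD at combination week 8 the ratios are 14/10 = 1.4 and 28/10 = 2.8. The last column needs three things that the documents leave open: that a patient who has already progressed is rescanned, that the scan precedes alternate therapy, and that it meets row 1's schedule condition. On the last, 26 − 8 = 18 weeks between scans, against 8-weekly scanning and the 3-month gap limit in row 2.

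**3. Size in a cohort (illustration only)**

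The documents state no PFS rate. Assume exponential times with median time to progression 10 weeks and median post-progression survival 16 weeks, scans at weeks 8, 16, 24 and so on, and 25% of progressors rescanned at 4 weeks. Let S(t) = 2^(−t/10).

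- 6-month (week 26) PFS, first-PD dating: about S(24) = 2^(−2.4) = 0.189.
- Literal row 1 adds patients whose PD appears at week 24 and who are rescanned at week 28: S(16) − S(24) = 0.3299 − 0.1895 = 0.1404; times 0.25 = 0.035; times survival for about 8 weeks after progression, 2^(−8/16) = 0.707, gives 0.025. The rate becomes about 21.4%. Simulation gives 18.9% to 21.3%, or about 22% if survival to the repeat scan is not required.
- Median, first-PD dating: just before week 16 the curve is near 0.535 (S(8) = 0.574, less about 0.039 for deaths before the scan). After week 16 it is 0.330, so the median is 16 weeks.
- Median, literal row 1: after week 16 the curve is at most 0.330 + 0.25 × (0.574 − 0.330) = 0.391. The median is still 16 weeks.

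The median is sensitive to the scan grid. With an assumed median PFS of 16 weeks, scans at weeks 10, 18 and 26 from first dose and the same 25%, the curve after week 18 is 0.4585 with first-PD dating and 0.4585 + 0.25 × (0.6484 − 0.4585) = 0.506 with row 1, so the median steps from 18 to 22 weeks. Over assumed medians of 10 to 26 weeks and 10% to 50% rescanned, the 4-week scan adds 1 to 6 points to the 26-week rate.

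**4. How often the missing row could matter (illustration only)**

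With assumed median PFS of 10 to 16 weeks and post-progression survival of 8 to 26 weeks, 54% to 90% of progressors would be dead by 1 year and 86% to 100% by 2 years.

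**5. Primary design**

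The Simon rule (0/13 stop, at least 4/27 reject) reproduces: early stop at 5% is 0.95^13 = 0.513 (stated 51%), type I error is 0.042, and power at 20% is 0.801 (stated 80%). None of it uses PFS.

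**The case against.** The strongest reply is that the first-progression rule is stated several times, including in the statistical section, and that the form collects the first date. A careful analyst would use it. The patients given the 4-week repeat scan are exactly those whom 4.9 and 12.3.2 date back to the initial event. Progression followed by death is a PFS event at progression under the text of 8.3.6. This largely stands: longer PFS arises only if the table is coded literally over the text.

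It does not remove the contradiction. The table is introduced as the calculation rule, and no order of precedence is given. The explicit dating rule in 4.9 and the backdating in 12.3.2 are written for patients who continue treatment; those who stop at PD rest on the general definitions and the form.

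A reader might go further in two ways that the documents do not support:

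- **That reported PFS will be badly inflated.** Under the step 3 assumptions, plus a 6-month scan in every early stopper alive then, a simulation can move the median from 16 to about 25 weeks and 6-month PFS from 19% to 34%. That applies row 1 to patients who later die, despite its alive condition. It also ignores the exclusion of scans after alternate therapy, and treats an 18-week scan gap as on schedule. Nor is it settled that progressed patients get the 6-month scan: footnote 23 follows those who stopped for PD by phone or email for survival, although its note covers all early stoppers.
- **That progression followed by death has no rule at all.** It has no table row, but the text definition covers it.

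**Conclusion.** The point holds as an internal contradiction with a missing scenario. Row 1 gives the wrong date for a progression whenever a countable scan follows it, and the table omits patients who progress and then die. The direction under literal coding is certain: a later scan can only lengthen PFS. The firm per-patient figure is 14 weeks instead of 10 for PD at combination week 8 with the repeat scan; about 28 weeks is possible but depends on the three uncertain conditions above. No population shift in median PFS should be claimed, because every cohort figure rests on assumed progression and survival times. This should be fixed before analysis. It concerns a descriptive secondary endpoint with no hypothesis test.

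**What to change.** In row 1 of Table 8.3.2, separate the two outcomes:

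- **PD documented:** event = 1; PFS time = date of the first scan meeting RECIST 1.1 PD minus the start date, whatever scans or death follow. Remove the alive condition for this case.
- **No PD, alive:** event = 0; PFS time stays at the latest tumor assessment.

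This brings the table into line with the text of 8.3.6 and with 4.9, 6.2.1 and 12.3.2. It changes two cells and needs no new data, because section 6.2.1 already has the first PD date recorded.

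### PFS is defined with two time origins and two rules for deaths without a recent scan, and the rows of Table 8.3.2 give some deaths two codings and others none

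*Combined protocol and SAP*

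**What the plan says.** Section 8.3.6 defines PFS as the "duration of time from start of treatment to time of progression per RECIST1.1 or death whichever comes first". It then introduces Table 8.3.2 as the rule for deciding events and calculating times. Four of its six rows, the third to the sixth, deal with deaths:

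- **Row 3** (scans available, no progression seen): event at death if the "patient dies before the next scheduled scan + 1 month".
- **Row 4** (scans available, no progression seen): censored at the latest scan if death comes more than 3 months after it.
- **Row 5**: "No post-treatment scan is available and patient dies before the first scheduled scan + 1 month". Event at death.
- **Row 6**: "No post-treatment scan is available and patient is lost follow up or patient dies >3 months later after starting treatment". Censored, with PFS time 0.

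Section 12.3.2 defines PFS as the "time from cycle 1, day 1 of immunotherapy until first documented local progression or death due to any cause" and adds: "Individuals will be censored at the date of the last scan for PFS if no event occurs". It has no missed-scan rule for deaths. It also does not repeat the 8.3.6 rule that patients who start alternate therapy before progressing are censored at their latest prior assessment.

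Section 8.2 ties starting treatment to a dose of entinostat. Section 4.1 puts the entinostat lead-in 2 weeks before the combination. The study calendar sets the first restaging 8 weeks after the combination starts, then every 8 weeks for 6 months, with 12-weekly scans allowed after that.

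**The concern.** Both prose definitions treat death as an event, but the table turns two kinds of known death into censored observations, one of them with no follow-up at all. Section 12.3.2 contains no such exception, and the two sections start the clock on different days. The table's event rows end at a scheduled scan plus 1 month, while its censoring rows start at a fixed 3 months. These limits coincide only by accident, so some deaths may fit two rows or none.

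PFS at 6, 12 and 24 months is a named secondary objective and endpoint. With 27 evaluable patients per cohort, one patient is 1/27 = 3.7 percentage points. Two analysts following the plan faithfully could report different PFS curves from the same data.

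**Working it through.** The plan states no figure on this point, so there is none to reproduce. The check is day arithmetic on the table rows, then an illustration of size.

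**Inputs.** Lead-in 14 days (4.1). First scan 56 days after C1D1; later intervals 56 or 84 days (study calendar). Convention assumed here: 1 month = 30.4 days, 3 months = 91.3 days.

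**Rows 3 and 4, days since the last scan.** The event row ends at interval + 1 month. The censoring row starts at 3 months.

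- 8-weekly: 56 + 30.4 = 86.4, against 91.3. Gap of 4.9 days: deaths at about days 87 to 91 fit neither row.
- 12-weekly: 84 + 30.4 = 114.4, against 91.3. Overlap of 23.1 days: deaths at about days 92 to 114 are both an event at death and censored at the last scan.

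**Rows 5 and 6, no scan.** The event row ends at the first scheduled scan + 1 month.

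- From the first entinostat dose: 14 + 56 + 30.4 = 100.4, against 91.3. Overlap of 9.1 days: deaths on about days 92 to 100 are both an event and a day-0 censoring. With 1 month taken as 28 to 31 days and 3 months as 84 to 92, the overlap runs from 98 − 92 = 6 to 101 − 84 = 17 days.
- From C1D1: 56 + 30.4 = 86.4, against 91.3. Gap of 4.9 days. It becomes a short overlap only if 3 months is read as 84 days or the +7-day scan window is used.

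**Size at 6 months (illustration; s and k are assumed).** Take N = 27 and s = 5 or 8 patients event-free at 6 months when all deaths are events, with no other censoring. That gives 5/27 = 18.5% and 8/27 = 29.6%. Let k patients be censored at day 0 under row 6.

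- If those k died before 6 months, the table gives s/(N − k). For k = 1: 5/26 = 19.2% and 8/26 = 30.8%. For k = 4: 5/23 = 21.7% and 8/23 = 34.8%. The shift is **up** by 0.7 to 5.2 points.
- If those k died after 6 months, the table gives (s − k)/(N − k). For k = 1: 4/26 = 15.4% and 7/26 = 26.9%. For k = 2: 3/25 = 12.0% and 6/25 = 24.0%. The shift is **down** by 2.7 to 6.5 points.

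A simulation gives a mixed case, with exponential times and three assumed ranges: median time to progression 2 to 3 months, median survival after progression 2 to 4 months, and 10 to 40% of patients deteriorating without a progression scan. Six-month PFS under the table was about 1 to 11 points below the version with all deaths as events.

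**The case against.** The strongest reply is that censoring after a long unscanned interval is a recognised choice, and that 8.3.6 presents the table as its own operational definition. Read that way, 8.3.6 is a general sentence followed by specific rules, and a death that fits no row can default to the sentence. This stands as far as 8.3.6 alone goes. It does not settle the conflict with 12.3.2, which has no such rule, nor does it decide a death that fits two rows.

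The table may also be closer to true progression. In the simulation above, with progression at a median of 2 months, survival after it of 4 months and 40% unscanned, true 6-month PFS was about 12%. The table gave about 20% and all deaths as events about 31%. Counting unscanned patients as progression-free until death can therefore overstate PFS. This argues for reporting both versions, not for leaving the choice open.

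The plan also limits missing scans. The calendar requires restaging near month 6 for patients who stop study drug earlier, and 8.3.3 asks for efforts to document progression after discontinuation. These help, but not for patients who die first.

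Two stronger readings are tempting:

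- A reader might infer that a death without a scan is always liable to be both an event and a day-0 censoring. The overlap is about 9 days wide and needs the entinostat origin; from C1D1 it is mostly a gap. Under the simulated assumptions, well under one patient per 27 would fall in it.
- A reader might infer from "until first documented local progression or death due to any cause" that distant progression is not counted. The next sentence in 12.3.2 applies RECIST 1.1, under which any new lesion is progression, and local may simply mean assessed at the site.

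**Conclusion.** The inconsistency holds on the text and needs no assumption: two time origins, two treatments of late deaths, and no stated precedence between 8.3.6 and 12.3.2. The failure of the rows to partition follows from the plan's own scan schedule. The widest fault is the overlap of about 23 days on 12-weekly scans. The day-0 overlap is narrower and depends on the origin.

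The numerical effect is not established. A reader might infer that the table biases PFS in a known direction, but the documents give no rate or timing of unscanned deaths. Several points up or down at 6 months is possible, depending mainly on whether the censored deaths fall before or after 6 months. PFS is a descriptive secondary endpoint in a single-arm trial, so the two-stage ORR decision is untouched. The wording should be corrected before PFS is analysed.

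**What to change.** 1. Use one time origin for PFS in 8.3.6 and 12.3.2.
2. State that the definition shared by the 8.3.6 text and 12.3.2 governs the primary PFS analysis: RECIST 1.1 progression or death from any cause, dated at the event. Keep the 8.3.6 censoring at alternate therapy and state it in 12.3.2 too.
3. Keep the Table 8.3.2 missed-scan censoring as a pre-specified sensitivity analysis. Use a single cut-off, for example the next scheduled scan plus 1 month, in both the event row and the censoring row, so that every death falls in exactly one row.
4. Report how many deaths the two versions code differently, because the all-deaths version can itself overstate PFS in unscanned patients.
5. In 12.3.2, replace local progression with progression per RECIST 1.1 as assessed by the investigator.

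The cost is rewording in two sections and one extra sensitivity analysis. No new data are needed.
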